APPENDIX B: NET Computable Phenotype – technical specification (SAS code)

NET-PRO Computable Phenotypes and Approaches for Recruitment

Overview

The NET-PRO recruitment approach is similar to the [ADAPTABLE](#) pragmatic clinical trial. Teams at each site will contact potentially eligible patients by electronic/ground mail or will approach them in person at the clinic. Understandably, each site may have a preference for a particular form of contact that will optimize their enrollment.

In order to accommodate these varied approaches, we have developed a multi-pronged approach that leverages existing data sources to identify potential enrollees. They include:

- Phenotypes that use diagnosis codes in electronic health record (EHR) data in clinical data research warehouses or most recent PCORnet Common Data Model (CDM) refresh.
 - A phenotype is provided for using these data for low-touch recruitment: ‘High positive predictive value phenotype’
 - A phenotype is provided for use when resources can confirm eligibility first, e.g. chart review or in clinic recruitment: “High sensitivity phenotype”
- Phenotypes that use data from institutional tumor registries
 - These data have a typical lag time of one year (depending on the institution), but an excellent phenotype is provided for using this data source as part of a low-touch recruitment strategy

This document describes the advantages and disadvantages of each data source and provides technical specifications for computable phenotypes that are appropriate for different recruitment strategies. For example, study sites that plan to recruit from their clinics or conduct chart reviews before recruiting may find it most effective to use a highly sensitive phenotype to identify potential participants and verify eligibility through chart review or in the context of a clinic visit; staff could screen out the false positives that would be flagged with such a phenotype. Sites that plan to recruit by ‘low-touch’ via e-mail or ground mail *without prior chart review to confirm eligibility*, however, will need a phenotype with high positive predictive value (PPV) to maximize the possibility that contacted patients actually have a neuroendocrine/carcinoid tumor (NET) diagnosis. (There is generally a trade-off between PPV and sensitivity; higher PPV is associated with lower sensitivity and higher sensitivity is associated with lower PPV.)

The validity of each computable phenotype is also discussed. Where available, results from validation studies performed at the University of Iowa Coordinating Center (UICC) are provided. Each site is encouraged to conduct its own validation studies, and the UICC can provide assistance for this based on its experience.

It is useful to remember that prospective enrollees will confirm their eligibility by responding to eligibility questions early in the enrollment process. This will serve as a final check in case the phenotype mistakenly identifies someone as having a qualifying NET. The recruiting materials have been worded carefully to minimize the possibility that a potential enrollee is alarmed to be contacted for a study focused on NETs.

Following the ADAPTABLE example, the UICC will continue to develop and refine these computable phenotypes to maximize their performance. This will happen through the life of the project.

Phenotypes that use diagnosis codes in electronic health record (EHR) data (research warehouse or CDM)

Many research institutions maintain medical record and billing data in a clinical research data warehouse (CRDW) that contains structured information on diagnoses and procedures. The PCORnet Common Data Model (CDM) is often populated by this source data. Computable phenotypes can be applied to the CDM or the underlying CRDW (which may be updated more frequently than the CDM).

An advantage of CRDW data is that patient data are structured by clinical or billing staff in real-world settings using the International Classification of Diseases (ICD) system (9th and 10th editions). While data are generally high quality, errors can occur. Also, diagnoses can change or be refined over time, and these changes are not always clearly documented. Some ICD codes are ambiguous with regard to tumor site (see the ICD codes labeled AMBIGUOUS in the Appendix). It is also important to note that the date a cancer ICD diagnosis code first appears on an encounter cannot necessarily be considered to be the date of cancer diagnosis; it generally lags behind the true diagnosis date. That lag in time can be substantial, especially if a patient was originally diagnosed or treated at another institution.

Phenotype for low-touch recruitment (without prior chart review or clinic visit): ‘High positive predictive value phenotype’

- This phenotype was designed to maximize positive predictive value so it would be appropriate for recruitment via electronic or ground mail without prior confirmation of eligibility through chart review or clinic visit.
- The phenotype identifies patients with at least one ICD code in their electronic medical record (EMR)/billing records that specifies a GEP or lung NET. To mitigate the effect of incidental coding errors, at least two NET codes (which may or may not specify the site of the NET; see code descriptions in the Appendix) must be present, and the patient’s first and last NET code must be more than 30 days apart.
- The first NET code for a patient is presently required to be dated on or after 01JAN2019. This increases the likelihood that the patient’s NET diagnosis will be in the required 2019-2023 study window.
- This phenotype should be applied for all patients who are not known to have died.
- The lung NET High PPV phenotype had a PPV of 92% and the GEP NET High PPV phenotype had a PPV of 90-98% when compared with chart review at The University of Iowa. The estimated sensitivity was 59.0% and 45.2%, respectively (see Technical Details Box 1 for further information)

Technical Details Box 1. Performance of Phenotypes that use Diagnosis Codes in EHR Data (research warehouses or CDM)

1. High PPV Phenotype

Estimating the Positive Predictive Value of the High PPV Phenotype

The University of Iowa (UI) team conducted a chart review to validate a 15% random sample of cases identified with this phenotype over a five-year period. This was done separately for lung (N = 13) and GEP NETs (N = 51).

- Of the 13 cases identified by the phenotype as having lung NETs, 12 had diagnoses that were unequivocally confirmed on chart review (i.e., the chart described pathological confirmation of a lung NET). This corresponds to a PPV of 92%. The single case that was not confirmed had a pancreatic NET.
- Of the 51 cases identified by the phenotype as GEP NETs, 46 had diagnoses that were unequivocally confirmed on chart review. This corresponds to a PPV of 90%. There were two other cases that had pathological evidence of a NET with an unknown primary location. An additional two cases had a suspected NET with no pathological confirmation on the chart. If these four cases are considered “hits”, PPV increases to 98%. For the one remaining case, the chart contained contradictory and ambiguous information about the patient’s tumor.

Estimating the Sensitivity of the High PPV Phenotype

The UI team used the University of Iowa Hospitals and Clinics (UIHC) institutional tumor registry to identify cohorts of patients with confirmed GEP and lung NETs (N = 166 and N = 39, respectively). These cases were diagnosed over a two-year period. The phenotype was applied to these cohorts to obtain a measure of sensitivity.

- Of the 39 cases with lung NETs, 23 cases were identified with the phenotype. This corresponds to sensitivity of 59.0%.
- Of the 166 cases with GEP NETs, 75 cases were identified with the phenotype. This corresponds to sensitivity of 45.2%.

2. High Sensitivity Phenotype**Estimating the Sensitivity of the High Sensitivity Phenotype**

As above, the UI team used the UIHC institutional tumor registry to identify separate cohorts of patients with confirmed GEP and lung NETs (N = 166 and N = 39, respectively). The high sensitivity phenotype was applied against these cohorts to obtain a measure of sensitivity.

- Of the 39 cases with lung NETs, 33 cases were identified with the phenotype. This corresponds to sensitivity of 84.6%.
- Of the 166 cases with GEP NETs, 148 cases were identified with the phenotype. This corresponds to sensitivity of 89.2%.

Implementation for high PPV phenotype

Definitions

%LET GEPCODES10 =

'C7A.01','C7A.010','C7A.011','C7A.012','C7A.019','C7A.020','C7A.021','C7A.022','C7A.023',
'C7A.024','C7A.025','C7A.026','C7A.029','C7A.092','C7A.094','C7A.095','C7A.096','C25.4';

%LET GEPCODES09 = '209.00','209.01','209.02','209.03','209.10','209.11','209.12','209.13','209.14',
'209.15','209.16','209.17','209.23','209.25','209.26','209.27','157.4';

%LET LUNGCODES10 = 'C7A.090';

%LET LUNGCODES09 = '209.21';

%LET ambiguousNET10 = 'C7A.00','C7A.098','C7A.1','C7A.8';

%LET ambiguousNET09 = '209.20','209.29','209.30';

Criterion	Logic/Notes	Defined
1. At least one ICD code that specifies a GEP or lung NET	Basis: CDM DIAGNOSIS table or source data equivalent	At least one record for each patient: Lung NETs (DX_TYPE = '09' AND (DX IN (&LUNGCODES09))) OR (DX_TYPE = '10' AND (DX IN (&LUNGCODES10))); GEP NETs (DX_TYPE = '09' AND (DX IN (&GEPCODES09))) OR (DX_TYPE = '10' AND (DX IN (&GEPCODES10)));

2. Patient's first NET code dated on or after 01JAN2019	Basis: CDM DIAGNOSIS table or source data equivalent	
Define first_net_dt:
 
Lung NETs [set of lung/ambiguous site NET records] → (DX_TYPE = '09' AND (DX IN (&LUNGCODES09,&ambiguousNET09))) OR (DX_TYPE = '10' AND (DX IN (&LUNGCODES10,&ambiguousNET10)));
 
GEP NETs [set of GEP/ambiguous site NET records] → (DX_TYPE = '09' AND (DX IN (&GEP09,&ambiguousNET09))) OR (DX_TYPE = '10' AND (DX IN (&GEP10,&ambiguousNET10)));
 
first_net_dt = of the set of lung/GEP NET records for each patient, min(admit_date)
 
***
 
first_net_dt >= '01JAN2019'd

3. Days between patient's first and last NET code is greater than 30 days	Basis: CDM DIAGNOSIS table or source data equivalent	
Define first_net_dt and last_net_dt:
 
Lung NETs [set of lung/ambiguous site NET records] → (DX_TYPE = '09' AND (DX IN (&LUNGCODES09,&ambiguousNET09))) OR (DX_TYPE = '10' AND (DX IN (&LUNGCODES10,&ambiguousNET10)));
 
GEP NETs [set of GEP/ambiguous site NET records] → (DX_TYPE = '09' AND (DX IN (&GEP09,&ambiguousNET09))) OR (DX_TYPE = '10' AND (DX IN (&GEP10,&ambiguousNET10)));
 
first_net_dt = of the set of lung/GEP NET records for each patient, min(admit_date) last_net_dt = of the set of lung/GEP NET records for each patient, max(admit_date)
 
***

		if intck('day',first_net_dt,last_net_dt) > 30
--	--	---

Phenotype for use when resources can confirm eligibility first, e.g. chart review or in clinic recruitment:
“High sensitivity phenotype”

- This phenotype was designed to maximize sensitivity so it would be appropriate for clinic recruitment or chart confirmation prior to e-mail or ground mail recruitment.
- The phenotype relaxes the criteria described above and identifies patients with at least one ICD code in their EMR/billing records that specifies a NET (see codes in the Appendix).
- Relaxing the number of codes required resulted in a sensitivity of 84.6% (lung) and 89.2% (GEP)(See Technical Details Box 1).

Implementation for high sensitivity phenotype

Criterion	Logic/Notes	Defined
1. At least one ICD code that specifies a NET	Basis: CDM DIAGNOSIS table or source data equivalent	At least one record for each patient: Lung NETs (DX_TYPE = '09' AND (DX IN (&LUNGCODES09,&ambiguousNET09))) OR (DX_TYPE = '10' AND (DX IN (&LUNGCODES10,&ambiguousNET10))); GEP NETs (DX_TYPE = '09' AND (DX IN (&GEPCODES09,&ambiguousNET09))) OR (DX_TYPE = '10' AND (DX IN (&GEPCODES10,&ambiguousNET10)));
2. Patient's first NET code dated on or after 01JAN2019		Lung NETs [set of lung/ambiguous site NET records] → (DX_TYPE = '09' AND (DX IN (&LUNGCODES09,&ambiguousNET09))) OR (DX_TYPE = '10' AND (DX IN (&LUNGCODES10,&ambiguousNET10))); GEP NETs [set of GEP/ambiguous site NET records] → (DX_TYPE = '09' AND (DX IN (&GEPCODES09,&ambiguousNET09))) OR (DX_TYPE = '10' AND (DX IN (&GEPCODES10,&ambiguousNET10)));

		<pre> first_net_dt = of the set of lung/GEP NET records for each patient, min(admit_date) *** first_net_dt >= '01JAN2019'd </pre>
--	--	--

Adding Data from Institutional Tumor Registries to Expand Low-Touch Recruitment

All hospitals at NET-PRO participating sites are accredited by the American College of Surgeons' Commission on Cancer (CoC). To maintain this accreditation, they are required to maintain a tumor registry. These registries identify tumors with malignant behavior and abstract their clinical characteristics, patient demographics, and treatment. This work is performed in compliance with the standards developed by the North American Association of Central Cancer Registries (NAACCR). Tumor registries document incident, primary cancers. Cases are documented by trained abstractors who gather information directly from patient medical records. The information is considered to be of high quality; registry records of NETs can be regarded with high confidence. Patients identified through this source could be approached for recruitment through e-mail or similar methods without necessitating prior chart review or clinic visit to confirm eligibility. Documentation is extensive and complies with NAACCR standards. Cancer site and histology are coded according to the International Classification of Diseases for Oncology, 3rd Edition (ICD-O-3). These standards allow for implementation of consistent case criteria across study sites.

When present in tumor registries, the diagnosis can be considered confirmed. However, there is usually a lag between diagnosis and case abstraction; cases are typically abstracted 4-6 months after diagnosis, and it can take more than a year before a registry abstracts all eligible cases for a given diagnostic year. Another limitation is that tumor registries generally abstract only those cancers that are diagnosed or treated at their respective institutions. Patients who are seen for tests only, a "second opinion", or other consultation may not be abstracted. So although documentation of a case can be regarded with high confidence, there are likely other eligible cases whose records are not abstracted. At the University of Iowa Hospitals and Clinics (UIHC), we have found that about two-thirds of eligible NET cases are found in tumor registry records. We have also found that about 45-59% of patients detected with the EHR High PPV phenotype (described in the previous section) are found in the tumor registry records. Hence, tumor registry data can be potentially useful to increase the number of patients for low touch recruitment, and this phenotype could be used in conjunction with the High PPV phenotype to increase eligible cases

Phenotype for using tumor registry data as part of a low-touch recruitment strategy

- This computable phenotype selects those patients with primary lung or GEP NETs diagnosed between 2019 and 2023 who are 18 years of age and older at diagnosis.
- Cases have been documented by trained abstractors who gather information directly from patient medical records. The information is considered to be of high quality.
- The unique patients identified by the tumor registry algorithm can be directly recruited without need for chart confirmation or clinic visit.

Implementation

Criterion	Logic/Notes	Defined
1. Lung/GE	Basis: CDM	Lung tumor site PRIMARY_SITE_N400 in ('C340','C341','C342','C343','C348','C349');

Criterion	Logic/Notes	Defined
P tumor site	
TUMOR table or source data equivalent (NAACCR #400 - Primary Site)
 
Sites that use the PCORnet tumor table must establish a link to a table with the identifying data that is necessary for recruitment; the tumor table itself is deidentified.
 
Tumor registries generally do not store the decimal in the ICD-O-3 site codes, but this may vary between hospitals.
	
GEP tumor site PRIMARY_SITE_N400 in ('C160','C161','C162','C163','C164','C165','C166','C168','C169','C170','C171','C172','C173','C178','C179','C180','C181','C182','C183','C184','C185','C186','C187','C188','C189','C199','C209','C250','C251','C252','C253','C254','C257','C258','C259','C260','C268','C269');

Criterion	Logic/Notes	Defined
2. NET histology	
Basis: CDM TUMOR table or source data equivalent (NAACCR #522)
 
Some sites may store histology in the first four characters of the morphology variable (NAACCR #521 Morph--Type&Behav ICD-O-3). This variable is not included in Version 1.2 of the PCORnet tumor table.
	
HISTOLOGIC_TYPE_ICD_O3_N522 in ('8150','8151','8152','8153','8155','8156','8157','8240','8241','8242','8246','8249');

3. Diagnosed between 01/01/2019-12/31/2023	
Basis: CDM TUMOR table or source data equivalent
	
substr(DATE_OF_DIAGNOSIS_N390,1,4) in ('2019', '2020', '2021', '2022', '2023');

Criterion	Logic/Notes	Defined
	(NAACCR #390)	
4. Aged ≥ 18 years at diagnosis	Basis: CDM TUMOR table or source data equivalent (NAACCR #230)	input(AGE_AT_DIAGNOSIS_N230,3.) ≥ 18 ;

Other Recruitment Methods

Direct recruitment of eligible patients attending clinic (i.e., recently diagnosed), or at a routine follow-up appointment (i.e., prevalent cases) (see Protocol 4.3.1).

This approach will require a liaison with the practice clinics to assess patient appointments and coordinate with the clinical team to introduce the study in-person and supply a study packet/e-mail invitation. Provision of specific guidance on this is difficult, as the process will differ according to the logistics of each site. Further guidance on this route will be disseminated and discussed with study coordinators and the recruitment monitoring workgroup.

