The Neuroendocrine Tumor – Patient Reported Outcomes (NET-PRO) project is a prospective cohort study of all newly occurring GEP and lung NET cases aged 18 years and older diagnosed between 01/01/2019 and 12/31/2023. Participants will be recruited across 14 participating Patient Centered Outcomes Research Network (PCORnet) sites (from across 4 PCORnet clinical research networks), enrolling an average of 215 patients per site over the 3-year study period (~3,000 patients total), allowing up to a maximum of 60 months of follow-up. Participants will complete four online (or paper) surveys over 18 months; these surveys will focus on patient-reported outcomes, including questions on quality of life, treatment decisions, and experiences with cancer care. These survey data will be linked to individual participant level tumor and clinical characteristics from medical record data.

Project specific aims:

AIM 1: To describe the frequency of treatment regimens and examine their association with symptom burden and PROs and HRQoL outcomes. Enroll a cohort of patients to collect HRQoL and PROs data every 6 months, for 18 months (i.e.: baseline, 6, 12 and 18 month follow-up surveys). We will determine what combinations of therapy are being used, and the changes in symptoms, PROs and HRQoL associated with these different therapeutic choices.

AIM 2: To examine the association of patient, clinical, and tumor characteristics on treatment choice. We will use EMR data to investigate the impact of pre-existing comorbidities (i.e.: cardiovascular, renal and liver disease and diabetes), prognostic tumor factors (derived from cancer registry data) i.e.: stage, grade and nodal status, on the selection of therapies received and outcomes of survival and disease progression (collected via targeted chart reviews).

AIM 3: To compare the effectiveness of peptide receptor radionuclide therapy (PRRT) regimens on outcomes of renal toxicity, disease progression, and patient symptoms and HRQoL. We will utilize the combined PROs gathered in aim 1 and EMR data mined in aim 2 (i.e.: predictors), to compare the effectiveness of various PRRT treatment combinations and sequences, on outcomes of reduced creatinine clearance (renal toxicity), HRQoL and symptom burden, and survival and disease progression. We will further study the heterogeneity of these treatment effects by grade of differentiation (G1/2 vs G3) and NET subsite (GEP vs lung).

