4.2. Inclusion/Exclusion Criteria

To be eligible for this prospective cohort study subjects must meet **all** of the following criteria:

- i. Incident GEP-NET/Lung NET diagnosis*(see [Appendix A](#))
- ii. Diagnosed 01/01/2019-12/31/2023
- iii. No known prior GEP-NET/Lung NET diagnosis
- iv. Aged ≥ 18 years at diagnosis
- v. At least one site encounter within the study period of January 1, 2019 to December 31, 2023

* See [Appendix A](#) for a full list of International Classification of Diseases, Ninth Revision, Clinical Modification (ICD-9-CM), The International Classification of Diseases, Tenth Revision, Clinical Modification (ICD-10-CM) codes used to define a NET diagnosis. This appendix also lists the ICD-O-3 site codes and eligible histology codes for implementation in tumor registry data sources.

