5.7.1. Patient-Reported Eligibility Criteria

Given the difficulty of specifying a computable phenotype in a rare disease like NET (i.e.: potential for false positives), and that the nomenclature for NETs can be uncertain, patient self-report will be used to verify the patient's belief that they have been diagnosed with a NET (and to ensure patients are not distressed by receiving the study invitation if they do not think they have a tumor). The language below has been drafted for review by the patient advisory committee and clinician group for use in the invitation to participate:

"You are receiving this study packet because your medical records indicate that you were evaluated in clinic for a possible neuroendocrine condition. If the neuroendocrine condition you were evaluated for was diagnosed as a neuroendocrine/carcinoid tumor, you may be eligible to participate in this study. To be eligible, you must have been diagnosed with a neuroendocrine tumor of the lung or bronchus and/or gastrointestinal tract (i.e.: stomach, duodenum, jejunum, ileum, colon, pancreas, rectum or appendix) on or after January 1, 2019. In addition, you must have been 18 years of age or older at the time of diagnosis. If the above criteria does not apply to you or you feel you've received this packet in error, please accept our apologies. In addition, please check the box and return the blank packet in the enclosed postage paid envelope."

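### No written step on the tumor-registry recruitment route applies inclusion criterion iii, so a patient with an earlier NET and a further primary in 2019-2023 can enter the incident cohort

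*Protocol*

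**What the plan says.** The synopsis describes a "prospective cohort study of all newly occurring GEP and lung NET cases aged 18 years and older". Section 4.2 lists five criteria, all of which must be met. The third is "No known prior GEP-NET/Lung NET diagnosis", and it covers either site. Section 4.1 sets the index date at diagnosis of the eligible tumor within the study period.

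Appendix B describes the registry query thus: "This computable phenotype selects those patients with primary lung or GEP NETs diagnosed between 2019 and 2023 who are 18 years of age and older". Its implementation table has four conditions: primary site, histology, diagnosis date and age. The date condition works on the year field of a record: "substr(DATE_OF_DIAGNOSIS_N390,1,4) in ('2019', '2020', '2021', '2022', '2023". On what follows selection, the appendix says: "The unique patients identified by the tumor registry algorithm can be directly recruited without need for chart confirmation or clinic visit".

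Appendix B relies on the patient's own confirmation of eligibility as the last check against a mistaken identification. The drafted text in section 5.7.1 reads "To be eligible, you must have been diagnosed with a neuroendocrine tumor of the lung or bronchus and/or gastrointestinal tract", with a date on or after January 1, 2019, and then "In addition, you must have been 18 years of age or older at the time of diagnosis". It has no question about an earlier NET.

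Both ICD-code phenotypes, unlike the registry query, do carry a first-code date rule. Their implementation tables list a lung-plus-ambiguous record set and a GEP-plus-ambiguous record set, and then define "first_net_dt = of the set of lung/GEP NET records for each patient, min(admit_date").

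**The concern.** Criterion iii is what makes this an incident cohort, and on the registry route nothing written carries it out. The query does not look for an earlier record, chart confirmation is waived, and the attestation does not ask.

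The consequence is a wrong time origin. PFS and OS run from the index date (section 7.2), treatments are ordered relative to it (section 7.1), and comorbidity is taken from the two years before diagnosis (Table 2). In a patient who already had a NET, earlier therapy, progression or toxicity lies before time zero. If that earlier tumor received therapy of a kind the study counts, a later line can be labelled first-line, which touches Aims 1 and 2. For Aim 3, baseline renal function may already reflect earlier treatment.

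**Working it through.** The protocol gives no figure to reproduce and no rate of prior NET, so the check is logical: apply the rules as written to hypothetical patients.

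**Registry route.** Rule: select if any record has a listed site, a listed NET histology, a diagnosis year in 2019-2023 and age at diagnosis of at least 18. All four patients are adults with listed histology.

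| Patient | Registry records | Meets criterion iii? | Selected? |
|---|---|---|---|
| A | Ileal NET 2020 | Yes | Yes |
| B | Ileal NET 2015; new lung primary 2020 | No | Yes |
| C | Ileal NET 2015; second ileal primary 2020 | No | Yes |
| D | Ileal NET 2015; recurrence only, no new record | No | No |

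B and C pass on the 2020 record because nothing examines the 2015 one. Both can truthfully attest to a NET diagnosed since January 1, 2019 and to adult age. D is not selected: Appendix B states that registries document new primaries, so a recurrence creates no record in the window. The gap is therefore a further primary after an earlier NET, and nothing wider.

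**ICD phenotypes.** Rule, with the first-code date taken within each site group plus ambiguous codes: select if there is at least one code of the required type and the earliest code in that set is on or after January 1, 2019. For the high-PPV version, assume that the requirement of more than 30 days between first and last code is also met.

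- Lung code 2015, lung code 2020: the lung-set minimum is 2015, so the patient is rejected.
- Ambiguous code 2015, lung code 2020: ambiguous codes belong to the lung set, so the minimum is 2015 and the patient is rejected.
- GEP code 2015, lung code 2020: the lung-set minimum is 2020, so the lung phenotype selects the patient, although criterion iii fails.

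Only an earlier site-specific code from the other site group escapes. The prose for the high-PPV phenotype speaks of the patient's first NET code without restricting it by site. That rule would reject the third patient, so prose and table can give different answers.

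**Later detection.** The chart review in section 6.2 covers every enrolled subject near the end of follow-up. Its named items are disease status, poorly populated CDM variables and other clinical or pathological characteristics. The date of the first NET and confirmation of eligibility are not among them.

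**The case against.** The strongest reply is that criterion iii remains binding whatever the query does. The phenotypes only propose potentially eligible patients, sites must screen as well as recruit (section 5.2.2), and they record how eligibility was assessed (section 5.9). The permission to recruit registry patients directly is not an order to skip screening. This is fair, but no step on that route tells anyone to look for an earlier NET, and the permission rests on the claim that registry identification suffices.

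The attestation is labelled a draft, and the phenotypes are to be refined throughout the project. That makes the repair easy; it does not make the present text right. The ICD part also depends on how the table is read, and the high-sensitivity version is meant to be followed by chart or clinic confirmation. That part is therefore the weaker one.

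Four stronger readings are tempting and are not supported:

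- A reader might infer that any patient with a past NET gets in. Recurrences alone are not selected.
- A reader might multiply the two-thirds registry share in Appendix B by 3,010, giving about 2,007 patients on this route. That share is one hospital's registry coverage of eligible cases, not the fraction recruited through the registry. With no rate of earlier NET either, no count follows.
- A reader might cite the 1 of 13 chart-reviewed lung-phenotype cases that proved to be a pancreatic NET. That is site misclassification, with no mention of an earlier NET.
- A reader might conclude that nothing could remove such patients later. The chart-review list is open-ended and its form is not yet built, CDM data reach back two years before diagnosis, and the baseline survey asks about past conditions and treatments. Some cases could surface, and exclusions from analysis may be set in a statistical analysis plan that is not shown.

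**Conclusion.** The point holds for the registry route: the written query and the written attestation both omit a criterion that section 4.2 makes mandatory, and chart confirmation is waived. A patient with an earlier NET and a further primary registered in 2019-2023 can enter with the later tumor as index. The ICD phenotypes have a narrower gap if the first-code date is computed by site group.

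The size is unknown and probably small, since it is limited to patients with a second primary NET. Line of therapy shifts only where the earlier NET received counted therapy; an earlier tumor that was resected and had no systemic or liver-directed treatment would not shift it. The conclusion assumes that sites follow Appendix B as written and add no prior-NET check of their own. The case for acting rests on the contradiction with the protocol's own definition and the low cost of repair, not on a demonstrated bias.

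**What to change.** 1. Add a registry condition: the patient's earliest record with a listed lung or GEP site and a listed NET histology, pooled across sites, is dated on or after 01/01/2019. Use that record as the index.
2. In both ICD phenotypes, compute the first-code date over the union of GEP, lung and ambiguous codes, so that the tables agree with the patient-level prose.
3. Add to the attestation that the patient had no lung or GEP neuroendocrine tumor diagnosed before January 1, 2019.
4. Put the date and site of the first NET on the chart-review form still to be developed (section 6.2.1). Exclude patients who fail criterion iii, or run a sensitivity analysis without them.

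Items 3 and 4 are needed alongside item 1 because, as Appendix B says, registries generally hold only cancers diagnosed or treated at their own institution, so a query cannot see an earlier NET managed elsewhere.

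The cost is a few lines of query code, one sentence in materials that need IRB approval, two fields on a form to be completed for every subject anyway, and the loss of a few patients.
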